# BORA Band SpO2 Validation Study PR 2018-312

# **Synopsis**

#### Introduction

The clinical use of pulse oximeters has reduced the frequency and necessity of invasive arterial blood sampling and has helped to improve patient safety by providing continuous information to clinicians about patients' oxygenation status.

BiOSENCY is dedicated to developing and applying innovative electronic medical solutions that improve clinical workflow and enhance patient care. The BORA BAND™ wristband Pulse Oximeter is to be used in continuous applications for monitoring oxygen saturation.

# **Objectives of the Clinical Investigation Plan**

The purpose of this clinical study is to validate the SpO2 accuracy of the BiOSENCY BORA BAND™ wristband Pulse Oximeter during non-motion conditions over the range of 70-100% SaO2 as compared to arterial blood samples assessed by CO-Oximetry. The end goal is to provide supporting documentation for the SpO2 accuracy validation of BORA BAND™ wristband Pulse Oximeter.

It is required that the Accuracy Root Mean Square (ARMS) performance of the BORA BAND™ wristband Pulse Oximeter will meet a specification of 3.5 or better in non-motion conditions for the range of 70 − 100% SpO2 thereby demonstrating an acceptable SpO2 accuracy performance specification.

# **Background**

Pulse oximetry monitoring is considered a standard physiological measurement and is used by clinicians in everyday situations to estimate arterial oxygen saturation. In general, pulse oximeters use two-wavelength absorption spectrophotometry to measure oxygen saturation. The wavelengths are selected to provide the best separation of absorbencies of oxy-hemoglobin ( $O_2$ Hb) and deoxy-hemoglobin (RHb) states. The ratio of the two absorbencies is used to calculate the oxygen saturation ( $SpO_2$ ) value. Because an arterial sample of blood is not required to make the measurement, the pulse oximeter can provide continuous non-invasive real time information. The clinical use of pulse oximeters has reduced the frequency and necessity of invasive arterial blood sampling and has helped to improve patient safety by providing continuous information to clinicians about patients' oxygenation status.

The BiOSENCY BORA BAND™ wristband Pulse Oximeter studied under this protocol will be investigational. All appropriate pre-clinical testing on the BiOSENCY BORA BAND™ wristband Pulse Oximeter system has been successfully performed and demonstrates safety and efficacy for use in human studies prior to Clinimark's receipt of the devices.

# **Summary Overview**

The SpO₂ accuracy performance of BiOSENCY BORA BAND™ wristband Pulse Oximeter will be evaluated during non-motion conditions over the range of 70-100% SaO₂ and compared to arterial blood samples assessed by CO-Oximetry. A minimum of 10 healthy adult male and female subjects, ranging in age and pigmentation from light to dark, will be enrolled in the study to meet the study design requirements defined by ISO 80601-2-61:2017 and by the FDA's Guidance for Pulse Oximeters (March 4, 2013). The

Clinimark, LLC	TITLE: BORA Band SpO2 Validation Study	DOCUMENT NUMBER	REV	1
[name]	Study ID# PR 2018-312	PR# 2018-312	1	Ì
[name], USA	Principal Investigator: [name] Site ID # 001	Page 3 of 36	1	Ì

subjects will have an arterial catheter placed in the radial artery to allow for simultaneous blood samples during stable plateaus of induced hypoxic levels. The investigational device will be placed on the wrist opposite for the test per the instructions for use. Simultaneous data collection will be set up for the system under test and control oximeter.

For the data analysis, the control oximeter will be used to assess the stability of each data point. Data that is found to be unstable will be removed prior to the comparative analysis. Data that is determined to be too low of perfusion will be removed. The CO-Oximeter data will be reviewed to make sure it does not contain any anomalous values such as elevated, low or inconsistent COHb, MetHb, or tHb data. Anomalous values will be removed from the analysis prior to pairing of the  $SpO_2$  and  $SaO_2$  data. The statistical analysis is performed on a minimum of 200 data points collected from at least 10 subjects for the range of 70% to 100%  $SaO_2$  with allowance of  $\pm$  3% of the target range. Functional  $SaO_2$  as measured by Reference CO-Oximetry will be used as the basis for comparison. The Accuracy Root Mean Square (ARMS) calculation is used to determine the  $SpO_2$  accuracy performance. Success will be achieved with an  $A_{RMS}$  of 3.5 or better showing equivalence to the Gold Standard Reference CO-Oximetry providing documentation to support  $SpO_2$  accuracy claims for the investigational device.

The study population will include 10-15 healthy non-smoking (or has refrained from smoking for 2 days) competent adults, 18-50 years of age. The subject selection will be an equitable distribution of males and females of any race with varying skin tones including at least 2 darkly pigmented subjects or 15% of the subject pool, whichever is larger. The subjects must understand the study and consent to participate by signing the Informed Consent Form. The subjects must be healthy showing no evidence of medical problems as indicated by satisfactorily completing the health assessment form.

#### **Inclusion Criteria**

- 10-15 Adults with a minimum of 3 males and a minimum of 3 females, with the balance made up of either
- Subject must have the ability to understand and provide written informed consent
- Subject is 18 to 50 years of age
- Subject must be willing and able to comply with study procedures and duration
- Subject is a non-smoker or who has not smoked within 2 days prior to the study
- Wrist size should be between 15-23 cm (5.9 9 inches)

#### **Exclusion Criteria**

- Subject is considered as being morbidly obese (defined as BMI >39.5)
- Compromised circulation, injury, or physical malformation of fingers, wrist, hands, ears or forehead/skull or other sensor sites which would limit the ability to test sites needed for the study. (Note: Certain malformations may still allow subjects to participate if the condition is noted and would not affect the particular sites utilized.)
- Female subjects that are actively trying to get pregnant or are pregnant (confirmed by positive urine pregnancy test unless the subject is known to be not of child-bearing potential).
- Smoker Subjects who have refrained will be screened for COHb levels >3% as assessed with a Masimo Radical 7 (Rainbow)
- Subjects with known respiratory conditions such as: (self-reported)
  - o uncontrolled / severe asthma,

Clinimark, LLC	TITLE: BORA Band SpO2 Validation Study	DOCUMENT NUMBER	REV
[name]	Study ID# PR 2018-312	PR# 2018-312	1
[name], USA	Principal Investigator: [name] Site ID # 001	Page 4 of 36	

- o flu,
- o pneumonia / bronchitis,
- o shortness of breath / respiratory distress,
- o unresolved respiratory or lung surgery with continued indications of health issues,
- emphysema, COPD, lung disease
- Subjects with known heart or cardiovascular conditions such as: (self-reported, except for blood pressure and ECG review)
  - hypertension: systolic >140mmHg, Diastolic >90mmHg on 3 consecutive readings (reviewed during health screen).
  - o have had cardiovascular surgery
  - o Chest pain (angina)
  - heart rhythms other than a normal sinus rhythm or with respiratory sinus arrhythmia (reviewed during health screen)
  - previous heart attack
  - blocked artery
  - o unexplained shortness of breath
  - o congestive heart failure (CHF)
  - history of stroke
  - o transient ischemic attack
  - carotid artery disease
  - o myocardial ischemia
  - myocardial infarction
  - cardiomyopathy
- Self-reported health conditions as identified in the Health Assessment Form (self-reported)
  - o diabetes,
  - o uncontrolled thyroid disease,
  - kidney disease / chronic renal impairment,
  - o history of seizures (except childhood febrile seizures),
  - o epilepsy,
  - history of unexplained syncope,
  - o recent history of frequent migraine headaches,
  - recent symptomatic head injury (within the last 2 months)
  - cancer / chemotherapy
- Subjects with known clotting disorders (self-reported)
  - history of bleeding disorders or personal history of prolonged bleeding from injury
  - history of blood clots
  - o hemophilia
  - current use of blood thinner: prescription or daily use of aspirin
- Subjects with severe contact allergies to standard adhesives, latex or other materials found in pulse oximetry sensors, ECG electrodes, respiration monitor electrodes or other medical sensors (self-reported)
- Subjects with severe allergies to iodine (only applicable if iodine is used)
- Subjects with severe allergies to lidocaine (or similar pharmacological agents, e.g. Novocaine)
- Failure of the Perfusion Index Ulnar/Ulnar+Radial Ratio test (Ratio < 0.4)
- Unwillingness or inability to remove colored nail polish from test digits.

Clinimark, LLC	TITLE: BORA Band SpO2 Validation Study	DOCUMENT NUMBER	REV
[name]	Study ID# PR 2018-312	PR# 2018-312	1
[name], USA	Principal Investigator: [name] Site ID # 001	Page 5 of 36	

- Other known health condition, should be considered upon disclosure in health assessment form
- Wrist size should be between 15-23 cm (5.9 9 inches)

Data collection will occur over a 3-5 day period for this study population. Follow-up with each subject will be conducted within 5 days following participation in the study and will be conducted via telephone, text or email.

# BORA Band SpO2 Validation Study PR 2018-312

# **Objectives of the Clinical Investigation Plan**

The purpose of this clinical study is to validate the SpO2 accuracy of the BiOSENCY BORA BAND™ wristband Pulse Oximeter during non-motion conditions over the range of 70-100% SaO2 as compared to arterial blood samples assessed by CO-Oximetry. The end goal is to provide supporting documentation for the SpO2 accuracy validation of the BiOSENCY BORA BAND™ pulse oximetry.

It is required that the Accuracy Root Mean Square (ARMS) performance of the BiOSENCY BORA BAND™ pulse oximetry will meet a specification of 3.5 or better in non-motion conditions for the range of 70 − 100% SaO2 thereby demonstrating an acceptable SpO2 accuracy performance specification.

# Identification and Description of the Investigational Device

An oximeter is a device used to transmit radiation at a known wavelength(s) through blood and to measure the blood oxygen saturation based on the amount of reflected or scattered radiation. Pulse oximetry monitoring is considered a standard physiological measurement and is used by clinicians in everyday situations to estimate arterial oxygen saturation. Because an arterial sample of blood is not required to make the measurement, the pulse oximeter can provide non-invasive real time information. The clinical use of pulse oximeters has reduced the frequency and necessity of invasive arterial blood sampling, and has helped to improve patient safety by providing continuous information to clinicians about patients' oxygenation status.

The BiOSENCY BORA Band is a wearable multi-parameter medical monitoring system, composed of a sensor head mounted on a wearable wristwatch-like module. Pulse oximetry data are produced by a reflective photoemitter/detector element which acquires data from the wrist.

The device under test will be connected over Bluetooth Low Energy to a mobile and/or PC application that will be in charge of collecting data over the air continuously during the hypoxia protocol. Collected data will include:

- Measured Heart Rate
- Measured Ratio of Ratios and/or SpO2 value
- Raw data coming from the sensor including PPG signal stored for offline process
   The accompanying acquisition software will be provided by BiOSENCY.

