# **Data Acquisition System for the Investigational Device**

The data from the investigational devices will be collected by the sponsor separate from the Clinimark automated data collection system.

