# **Design of the Clinical Investigation**

#### Method

This study is a comparative, single-center, non-randomized study with a minimum of 10 subjects. Each subject test is expected to take approximately 1.5 to 2 hours. The overall data collection process will occur over a 3-5 day period for this study population.

Subjects will be provided an IRB approved Informed Consent which covers the essential information in the protocol, ISO 14155 (as reference only) and applicable regulatory requirements for a non-significant risk medical device investigation. Subjects will be provided sufficient time to review the informed consent and have all questions answered regarding their participation before enrollment or conduct of study specific procedures. As applicable, subjects will be told about any new information that might change their decision to participate.

Subjects who have completed (signed and dated) the informed consent and health questionnaire form and meet inclusion criteria and none of the exclusion criteria will be enrolled in the study. If the Informed Consent Form (ICF) is amended/updated throughout the life-cycle of the study, a determination will be made as to whether the subjects who have completed the study need to reconsent by reviewing, signing and personally dating the updated ICF.

Clinimark, LLC	TITLE: BORA
[name]	Study ID# PR 20:
[name], USA	Principal Investig

REV

1

Qualified healthy volunteers will be enrolled into the study. Subjects will recline for the study. Reference sensor(s) will be placed on each subject to evaluate the SpO2 accuracy and performance. Shield material may be used between any adjacent finger sensors to prevent optical crosstalk.

Simultaneous data collection will be set up for device under test and the control pulse oximeter. The data from the test device will be collected by the sponsor or trained Clinimark Study staff. Data will be collected for 1 second intervals data analysis. The SpO2 accuracy of the test devices will be evaluated over the oxygen saturation range between 70-100%.

The investigational device will only be placed on the wrist. The control pulse oximeter may be alternated through fingers between subjects.

A photo or video may be recorded to document the study if acceptable with the subject. Photo or video may be used for internal purposes, such as training by the sponsor.

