# **Endpoint / Comparator**

The primary objective of this study is to validate SpO₂ accuracy performance of BiOSENCY BORA BAND™ wristband Pulse Oximeter by an Accuracy Root Mean Square (Arms) value. Reference CO-Oximetry will be used as the basis for comparison for the investigational device SpO₂ readings. The study population will include 10 to 15 subjects. The data for analysis will have approximately 200 data points equally distributed across the range of 70-100% by decade. All data will be used for the analysis unless a rational is provided for its removal. Possible reasons for data removal include, but are not limited to, unstable control, dashed or zero values, poor perfusion at the site, inconsistent or invalid CO-Oximetry values. Data that is found to not be useable will be removed prior to the comparative analysis. For the statistical analysis, the Accuracy Root Mean Square (ARMS) calculation is used to determine the SpO₂ accuracy performance providing documentation for the SpO₂ accuracy for the device under test during non-motion conditions.

There are no deviations expected from this investigation plan, should deviations be needed, discussions will be conducted with the sponsoring company and reported to the reviewing IRB per standard operating procedures.

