Ref = Reference CO-Oximetry SaO2 DUT = Device Under test SpO2

 $SpO_2$  accuracy will be evaluated for root-mean-square (rms) difference between the DUT and the reference for the specified  $SpO_2$  ranges (70-100%) and by  $SpO_2$  decade (90-100%, 80<90%, 70-<80%). The number of data points will be included for each statistic.

$$Arms = \sqrt{\frac{\sum_{i=1}^{n} (DUT_{i} - \text{Re } f_{i})^{2}}{n}}$$

The average difference is calculated to show the bias of the device under test as compared to the reference. The bias is calculated for the specified  $SpO_2$  ranges (70-100%) and by decade (90-100%, 80-<90%, 70-<80%).

$$Bias = \frac{\sum_{i=1}^{n} (DUT_{i} - \operatorname{Re} f_{i})}{n}$$

A least squares line (slope and intercept) will be generated for the overall range. The minimum and maximum deviations will be calculated from the reference.

Bland-Altman graphical plots, error ( $SpO_2 - SaO_2$ ) versus average  $SaO_2 + SpO_2$  will be generated with linear regression fit, mean, and upper 95% and lower 95% limits of agreement according to Section 3 of "Agreement Between Methods Of Measurement With Multiple Observations Per Individual" by Bland and Altman in 2007 Journal of Biopharmaceutical Statistics. Individual test subjects will be color coded in the Bland-Altman graphical plot.

Values for the population mean bias ( $\mu$ 0), between-subject variance ( $\sigma\mu$ 2) and within-subject variance ( $\sigma$ 2) will be calculated according to Section 3 of "Agreement Between Methods Of Measurement With Multiple Observations Per Individual" by Bland and Altman in 2007 Journal of Biopharmaceutical Statistics. Individual test subjects will be color coded in the Bland-Altman graphical plot.

Error plots (i.e., SaO2 versus (SpO2-SaO2) for both individual test subjects and all subjects pooled) will be generated.

Additionally, a scatter plot will be generated.

Test device outliers with a value >5% difference from the Reference CO-Oximeter will be discussed in the Final report per the FDA Guidance document for Pulse Oximeters.

Clinimark, LLC	TITLE: BORA Band SpO2 Validation Study	DOCUMENT NUMBER	REV
[name]	Study ID# PR 2018-312	PR# 2018-312	1
[name], USA	Principal Investigator: [name] Site ID # 001	Page 24 of 36	ᆂ

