# Data and Quality Management / Confidentiality

A checklist will be maintained identifying the contents of the Trial Master File / Project folder PFC# 2018-312

The subject's name and signature will be recorded on the Informed Consent, Health Assessment Form, Subject Follow-up, Clinician: Subject Flow Sheet form and a subject participation list. The data collection form will only use a subject number and initials for the day of the test along with subject demographics. A name will not be recorded on the case report form.

Records identifying the subject's name will be kept in a secured location with either a locked file or locked door. Access to these files will be on a limited basis. Potential reviewers of this information include: Clinimark representatives collecting the information and conducting the study, Medical Director for Clinimark, the U.S. Food and Drug Administration (FDA), Department of Health and Human Services (DHHS) agencies, Governmental agencies in other countries, Salus Independent Review Board and representatives of the Sponsor. This group may use the information to conduct independent audits and reviews to verify compliance of the regulatory requirements for these studies but not copy the information.

Clinimark, LLC	TITLE: BORA Band SpO2 Validation Study	DOCUMENT NUMBER	REV
[name]	Study ID# PR 2018-312	PR# 2018-312	1
[name], USA	Principal Investigator: [name] Site ID # 001	Page 26 of 36	4

Data files stored electronically will be associated with a subject based off of subject #, date and by filename recorded on the data collection forms. The original device electronic data files will be preserved in its original form. Data analysis will be performed as a separate electronic file.

Data files, data collection records with subject demographics and subject number may be additionally copied, (after de-identification, if applicable) reviewed and supplied to the commercial sponsor for the study or Contractors associated with Clinimark for data analysis purposes.

All study records will be stored for at least 2 years post the release of the product or project cancellation. The investigator will notify sponsor prior to destruction of study records. Other storage arrangements may be executed per contractual agreement between the sponsor and the investigator.

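### The plan does not require a device-computed SpO2 to be logged, or its algorithm fixed, before the sponsor can see SaO2, which leaves a route to bias in the only pass/fail criterion

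*Combined protocol and SAP*

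**What the plan says.** **What is recorded.** The section *Identification and Description of the Investigational Device* lists heart rate, then "Measured Ratio of Ratios and/or SpO2 value", then "Raw data coming from the sensor including PPG signal stored for offline process". It adds: "The accompanying acquisition software will be provided by BiOSENCY".

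**Who holds it.** *Data Acquisition System for the Investigational Device* states: "The data from the investigational devices will be collected by the sponsor separate from the Clinimark automated data collection system". The *Method* section is wider: "The data from the test device will be collected by the sponsor or trained Clinimark Study staff". Under *Data and Quality Management / Confidentiality*, data files and collection records may be copied, "reviewed and supplied to the commercial sponsor for the study or Contractors associated with Clinimark for data analysis purposes".

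**What is analysed.** Under *CO-Oximeter Data*, the test value in the A_RMS formula is given as "DUT = Device Under test SpO" (with subscript 2) and nothing more. *Endpoint / Comparator* says that reference CO-oximetry "will be used as the basis for comparison for the investigational device SpO₂ readings". *Pass / Fail Criteria* has one line: A_RMS of 3.5 or less over 70-100%.

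**Nearest safeguards.** The software or firmware version is recorded, original device files are preserved with analysis done in a separate file, and deviations from the statistical plan must be justified in the final report.

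**The concern.** A validation A_RMS describes the device only if the step from optical signal to SpO2 is settled before the reference values are known. Under the *and/or* in the collection list, the record may hold only a ratio of ratios and the raw signal. Someone must then convert these to SpO2 later, and the plan does not say who, when or with which calibration. The sponsor supplies the acquisition software, may collect the device files and may receive study data for analysis. No section makes that receipt conditional on SpO2 having been delivered first.

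If the conversion were adjusted with SaO2 in hand, A_RMS would measure how well a curve fits these roughly 200 pairs, not the accuracy of the device as supplied. The final report could not show a reader which of the two had happened. Recomputing offline would not clearly count as a deviation either, since the plan does not exclude it.

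**Working it through.** **1. The sections side by side.** The endpoint needs an SpO2 value from the device. The collection list can be met without one. No section states which algorithm version produces the analysed value, that the version is locked, or that SaO2 is withheld from the sponsor until SpO2 is delivered. Recording a firmware version does not by itself identify a conversion done offline.

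**2. The plan's own figure.** 10 subjects × 20 points = 200 pairs, which matches the stated minimum. The plan gives no power, alpha or error components.

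**3. What a refit removes.** Ignoring any trend with saturation, A_RMS² = bias² + between-subject variance + within-subject variance. An offset fitted to the study's own SaO2 removes the bias term in-sample. For an assumed true A_RMS of 4.0:

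- With bias 2.0 the remainder is √(16 − 4) = 3.46, just under 3.5.
- The offset alone brings the expected value to the limit when bias² = 16 − 12.25 = 3.75, that is, bias ≈ 1.94.
- With bias 0 there is nothing systematic to remove: √16 = 4.0.

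**4. Simulated pass rates.** Assumptions: 10 × 20 pairs, SaO2 uniform on 70-100, error = bias + subject effect + noise, true A_RMS 4.0, intraclass correlation (ICC) 0.4. The error variance is 16 − bias². The between-subject share is 0.4 of it and the within-subject share 0.6 (at bias 2: 4.8 and 7.2). The linear refit regresses SaO2 on SpO2. Figures are good to one or two percentage points.

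| Assumed bias | Algorithm fixed | Offset refit | Linear refit |
|---|---|---|---|
| 0 | 9-10% | 14-15% | 48% |
| 1 | 12% | 24-25% | 60% |
| 2 | 14-15% | 67-68% | 89-90% |

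- Varying ICC from 0.2 to 0.6 at bias 2 gives about 6-25% fixed, 67-68% offset and 84-95% linear.
- The linear column depends on the direction of fit. Regressing SpO2 on SaO2 and inverting gives about 16% at bias 0 and about 68% at bias 2, close to the offset column.

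**5. Other error structures.** With SaO2 uniform over 30 points, its variance is 30²/12 = 75, so an error slope adds slope² × 75 to A_RMS².

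| Bias, slope, between / within SD | True A_RMS | Fixed | Offset refit | Linear refit |
|---|---|---|---|---|
| 3, 0, 1.5 / 2.0 | √(9 + 2.25 + 4) = 3.9 | 18% | 100% | 100% |
| 3, 0, 2 / 3 | √(9 + 4 + 9) = 4.69 | 0.4% | 50% | 84% |
| 0, −0.3, 1.5 / 2.5 | √(6.75 + 2.25 + 6.25) = 3.9 | 3% | 4% | 24% |

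The pass rate rises in every case run. The rise is large when the failure is mainly bias and small for an offset refit when it is mainly random error or slope.

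**The case against.** The strongest reply is that the collection list is one bullet in a device description, while the endpoint and analysis sections describe device output. *Endpoint / Comparator* speaks of device readings and allows dashed or zero values to be removed. *CO-Oximeter Data* removes test values truncated at 100% and drop-outs. A bare ratio of ratios is not truncated at 100%. This stands as evidence of intent, but a value computed offline can also be zero or exceed 100%, and the origin of the analysed number is still undefined.

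Second, there is an audit trail: version recording, preserved original files, monitoring checks on filenames and oximeter channels, and the possibility that site staff collect the device data. This also stands. A later recomputation could be detected, but the trail does not fix the value beforehand, and the preserved files may hold only ratios and PPG.

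Third, calibration had its own earlier study, described under *Preliminary Investigations and Justifications of the Study*. That makes tuning on this dataset less natural, though no section says the algorithm was frozen afterwards.

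Fourth, the plan defers to an ISO annex and an FDA guidance document. Whether they settle this cannot be told from the documents.

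A reader might also infer that the sponsor could watch the errors accrue and choose when to stop between 10 and 15 subjects. The documents do not support making that part of the point: *Statistical Analysis* already makes no provision for an interim analysis.

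**Conclusion.** The gap holds as an open route to bias in the sole pass/fail criterion. The plan neither requires a device-computed SpO2 to be logged nor requires the algorithm to be fixed, or the SpO2 file delivered, before the sponsor can see SaO2.

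A reader might go further and infer that offline recomputation is planned, or that the study will pass a device that fails. The documents do not support either: their wording leans towards device output, and nothing says that recomputed values will decide pass or fail.

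The size cannot be stated from the documents. For an assumed true A_RMS of 4.0 and ICC 0.4, the pass rate is about 9-15% with a fixed algorithm and anywhere from about 14% (bias 0, offset only) to about 90% (bias 2, linear) after a refit to the same data. The upper end depends on a bias of 2.0, which happens to leave a residual SD just below the limit, and on the direction of the linear fit. It should not be quoted alone. The point merits a change before the study starts because it bears directly on the only decision rule and is cheap to close.

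**What to change.** - **Identification and Description of the Investigational Device:** replace *and/or* so that device-computed SpO2 must be logged, at the 1-second interval already given in *Method*. Ratio of ratios and raw PPG become supplementary.
- **CO-Oximeter Data, definition of DUT:** define it as the SpO2 output of the firmware and algorithm version fixed before the first subject and recorded on the case report form.
- **Data Acquisition System and Method:** reconcile the two statements on who collects the device data. Add that the site's analyst receives the unmodified SpO2 files before any SaO2 value is released to the sponsor.
- **Statistical Analysis:** label any SpO2 recomputed offline as exploratory and outside the pass/fail decision.

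The cost is protocol wording and an order of file transfer, with no added subjects or procedures. The sponsor gives up re-tuning on this dataset for the accuracy claim. In return, a passing result can be shown to come from a fixed algorithm.
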